### 3. Study Endpoints/Events/Outcomes

- 3.1. Primary Endpoint/Event/Outcome: Primary outcome focuses on the total opioid requirement (morphine equivalent per body weight) over the operative and post-operative PICU course (which may range upwards of 7 days in some transplant cohorts). The hypothesis is that magnesium sulfate use will decrease this dosage compared to controls, however measurements will be used to determine whether the intervention does not have any statistical difference as well (or even increases doses, which would be otherwise unexpected in the literature). We intend to pilot 30 prospective transplant patients (liver, TPIAT). Retrospective control data will consist of the last 60 transplants (30 liver, 30 TPIAT), which was determined based on original power analysis targets for a larger-based study anticipated in the future. The study will be stopped prematurely if during obligated data reviews it is determined that opioid needs are increasing. The study will also be halted if 2 patients develop clinically significant adverse reactions secondary to magnesium, at minimum until able to further review dosing and protocols. If arrhythmia (other than transient bradycardia), respiratory failure, or coma are encountered once (also deemed secondary to magnesium), the study will be halted immediately with that patient. Per above, if encountering more frequent anemia than typical post-transplant, the study will be halted to evaluate lab frequency's effect. The study will also be halted for further review if there is a dosing error. A list of data measures is provided in a secondary attachment with this protocol.
- 3.2. Secondary Endpoint(s)/Event(s)/Outcome(s): Secondary outcome data will evaluate total opioid use by post-operative day (i.e. POD#1, POD#2, POD#3, etc) to help determine any variance in effect based on proximity to the surgery as well. Secondary outcomes will also focus on other opioid variables, including amount of 'requested' (PRN) opioids versus what is scheduled. Secondary outcomes will also include opioid side effect data, since these would hypothetically be less if MgSO4 does indeed lessen opioid needs. We will collect 'pain scores' as well, however literature suggests these are often difficult to

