### ***SECONDARY OUTCOMES***

#### opioid variables

1. Morphine Equivalent daily variance (daily dose/kg on each post-op day)
2. Total days on IV opioids
  - will use post-operative day when IV opioid discontinued (i.e. POD#6)
3. Total days on any opioid
4. PCA variables
  - # of demands, # of deliveries (daily and total values)
  - # of escalations in infusion dose
5. Scheduled vs PRN dosing
  - scheduled dosing includes PCA infusion dose and scheduled IV or PO opioids
  - PRN includes PCA delivered doses and PRN opioids delivered

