### Standard Reporting

2. type of transplant received
3. age
4. weight
5. height
6. gender

*15.2. Power Analysis:* Power analysis was performed based on pediatric studies by Hutchins et al and Jabbour et al (see references section 24), indicating 90 patients in order to see a detectable difference of 20% between study groups with 80% power. This would detect a decrease of nearly 3.5 mg/kg over a 7 day PICU course, and seemed a reasonable target for our hypothesis. Given the progression of IND review, this number will be reduced to 60 for the retrospective cohort (renal transplants removed from study), and 30 for prospective cohort (typical target for pilot-based study), to simulate a pilot study rather than fully correlational study. Regardless, original power analysis is shown below:

n per group	Detectable difference between groups (Total 1st 7 days in morphine equivalent mg/kg)		Detectable difference between groups (% reduction in dose)	
	80% power	90% power	80% power	90% power
40	5.26	6.09	29	33
50	4.70	5.43	26	30
60	4.28	4.95	24	28
70	3.96	4.58	23	26
80	3.70	4.28	21	24
90	3.49	4.03	20	23
100	3.30	3.82	19	22
110	3.15	3.64	18	21
120	3.01	3.49	18	20

Based on a pooled SD estimate for total morphine equivalent dose first 7 days post-op of 8.3 mg/kg (Hutchins 2016), the table lists the minimum differences (in mg/kg) that are detectable with 80% and 90% power for various enrollment sizes. These differences are also presented in terms of the % reduction in total dose, based on an overall mean total dose of 15.5 mg/kg (Hutchins 2016). For comparison, a 29.5% reduction in total dose (first 48h) in ketamine + magnesium versus ketamine was observed in Jabbour 2014.

*15.3. Statistical Analysis:* The primary analysis will compare the total morphine equivalent dose per kg during the PICU stay between experimental and historical control groups. Total dose will be compared in both unadjusted analyses and adjusted analyses using linear models, with a covariate for study group and adjusting covariates for transplant type, age, and gender, to account for potential variation due to these factors. Distributional assumptions will be examined and data transformations will be used as appropriate. Secondary outcomes will be compared using similar approaches using generalized linear models for count

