## MEDICAL PROTOCOL (HRP-590)

PROTOCOL TITLE: Magnesium sulfate as adjuvant analgesia and its effect on opiate use by post-operative transplant patients in the pediatric ICU.

VERSION DATE: 06/09/2022

outcomes (total days on IV opioids, number of PCA demands and deliveries, number of infusion dose escalations, number of ileus events, days until first stool, emesis counts, number of days naloxone infusion required, PICU duration, number of days intubated, paravertebral block dose increases), categorical outcomes (ketamine use, presence of side effects), and continuous outcomes (FLACC, Pain Score). Longitudinal measurements of magnesium, other analgesics, ionized calcium, PTH, and creatinine levels will be analyzed using mixed effects models. Group summaries including means, standard deviations, and rates will be reported and group differences will be summarized as incidence rate ratios, odds ratios, or mean differences with 95% confidence intervals. Analyses will be conducted using the intent-to-treat principle; control group participants who underwent magnesium replacement (for hypomagnesemia or pre-designed post-transplant protocol) will be included in the control group, and experimental group participants with discontinuation of magnesium, if any, will be included in the experimental group. A two-sided 5% level result will be regarded as significant. Statistical analysis will be per statistician's updated STATISTICAL ANALYSIS SOFTWARE (also used in a previous pain study with TPIAT cohort).

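### Section 3.2 asks whether the opioid effect changes with time from surgery, but section 15.3 states no group-by-day test and names no longitudinal model for daily opioid dose

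*Combined protocol and SAP*

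**What the plan says.** Section 3.2 sets the aim of the by-day analysis: to "evaluate total opioid use by post-operative day (i.e. POD#1, POD#2, POD#3, etc) to help determine any variance in effect based on proximity to the surgery". The opioid variables listed in section 15.1 include the matching endpoint, "Morphine Equivalent daily variance (daily dose/kg on each post-op day".

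Section 15.3 compares the primary outcome in unadjusted analyses and in linear models "with a covariate for study group and adjusting covariates for transplant type, age, and gender". For the rest, "Secondary outcomes will be compared using similar approaches", with generalized linear models by outcome type. One sentence provides for repeated measurements: "Longitudinal measurements of magnesium, other analgesics, ionized calcium, PTH, and creatinine levels will be analyzed using mixed effects models". Daily opioid dose is not named in that sentence, nor in the lists of count, categorical and continuous outcomes. Group differences are to be reported with 95% confidence intervals, and "A two-sided 5% level result will be regarded as significant". No group-by-day term, joint test across days or early-versus-late contrast appears anywhere.

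**The concern.** Whether an effect varies with proximity to surgery is a question about the difference between daily effects. Separate daily comparisons do not answer it. A significant day beside a non-significant day is not evidence that the two effects differ. The days also come from the same children, so separate models give no standard error for a between-day difference.

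The question matters to the plan. Section 4.1 limits the infusion to 48 hours, while section 3.1 says the PICU course may reach 7 days or more, so a real change over time is plausible. Without a planned contrast, a statement that magnesium works early but not later could come from sampling noise, and a genuine change would have no valid test. This remains with complete data. A multiplicity correction would not cure it, because it would not supply the missing contrast.

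**Working it through.** **Inputs from the documents.** 30 prospective and 60 control patients; SD of the 7-day total 8.3 mg/kg; mean total 15.5 mg/kg; 20% planning effect; two-sided 5% (sections 15.2 and 15.3).

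**Assumed, because the documents give no figures.** Between-day correlation ρ of 0.3, 0.5 or 0.8; equal daily means, SDs and effects; normal doses; no missing days; no covariate adjustment.

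**1. The plan's own figure.** With 90 per group and 80% power, the normal approximation gives (1.960 + 0.842) × 8.3 × √(2/90) = 3.47 mg/kg. The t-based calculation gives 3.49, as tabulated in section 15.2. The SD and alpha are therefore as stated.

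**2. Effect.** 20% of the stated mean is 0.20 × 15.5 = 3.1 mg/kg. The section 15.2 table pairs 20% with 3.49 mg/kg, which is 22.5% of 15.5, so 3.49 is also tried below.

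**3. Daily scale.** With K days, the daily effect is δ = 3.1/K. For the total to have SD 8.3, the daily SD is σ = 8.3/√(K(1 + (K−1)ρ)). For K = 7 and ρ = 0.5:
- δ = 3.1/7 = 0.443 mg/kg
- σ = 8.3/√(7 × 4) = 1.569 mg/kg
- δ/σ = 0.282
- noncentrality = 0.282/√(1/30 + 1/60) = 0.282/0.2236 = 1.26, giving about 24% power on one day.

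**4. How often the days disagree.** In each simulated trial, every day was tested by a pooled t-test at 5%. The same data were analysed once by a group-by-day F test. The true effect was identical on every day.

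| Days | ρ | Daily SD | δ/σ | Power on one day | Some days significant, some not | Group-by-day test signals variation |
|---|---|---|---|---|---|---|
| 7 | 0.3 | 1.875 | 0.236 | 18% | 61% | about 5% |
| 7 | 0.5 | 1.569 | 0.282 | 24% | 60% | about 5% |
| 7 | 0.8 | 1.303 | 0.340 | 33% | 44% | about 5% |
| 3 | 0.3 | 3.788 | 0.273 | 23% | 44% | about 5% |
| 3 | 0.5 | 3.388 | 0.305 | 27% | 40% | about 5% |
| 3 | 0.8 | 2.972 | 0.348 | 34% | 28% | about 5% |

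Repeat runs of 5,000 to 10,000 trials agree within about 1.5 percentage points. With 3.49 mg/kg instead of 3.1, the days disagree in about 47 to 68% of trials with 7 days and 30 to 50% with 3 days.

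**5. What the replacement could detect.** Take 7 days, ρ = 0.5 and a 3.1 mg/kg total effect that halves after day 2. From 2a + 5(a/2) = 3.1, a = 0.689 early and 0.344 late, a difference of 0.344 mg/kg per day. The standard error of the early-versus-late contrast is √(0.05 × 1.569² × 0.5 × (1/2 + 1/5)) = 0.208, where 0.05 = 1/30 + 1/60. Then z = 0.344/0.208 = 1.66 and power is about Φ(1.66 − 1.96) = 38%. The 6-df interaction test on the same pattern has noncentrality 0.1695/(0.05 × 1.569² × 0.5) = 2.76, where 0.1695 is the sum of squared deviations of the daily effects from their mean. Its power is about 19%. If the whole effect fell on the first 2 days, the contrast would be 1.55 and z = 1.55/0.208 = 7.5, so either test would detect it.

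**The case against.** The strongest reply is that this is a gap in specification and not a documented wrong method. Section 15.3 never says that each day is tested separately, or that variation is judged by counting significant days. A reader might infer that the plan has adopted that rule. The documents do not support so firm a reading, and the disagreement rates above apply only if results are read that way. Planned 95% intervals also soften the problem, and section 3.2 says only that the daily data will help, in a study described as a pilot. These points stand. They do not supply the missing test: intervals for separate days still give no standard error for a difference between days.

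Could the phrase on other analgesics in the mixed-model sentence cover opioids? Section 3.2 lists opioid variables and other analgesic dosing as separate items, which suggests not. Even if it did, no interaction is stated.

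Two further inferences fail. A reader might apply 3.1/8.3 = 0.37 SD to every day and obtain disagreement rates of 46 to 84% with 7 days. That ratio belongs to the 7-day total. Used daily, it implies total effects of 0.37 × σ × 7 = 4.86, 4.06 and 3.37 mg/kg at ρ = 0.3, 0.5 and 0.8, or 31%, 26% and 22% of 15.5. A reader might also take daily dose to be the only evidence on timing. Section 15.1 also splits morphine equivalents into OR, PICU and overall, and lists daily PCA demands and deliveries.

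Finally, the 5% rate for the interaction test holds on the additive scale simulated. If opioid use falls over the stay, a constant percent effect gives shrinking mg/kg differences, and an interaction in mg/kg could flag them. This objection is sound, and the fix has to name the scale.

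**Conclusion.** The point holds as a missing analysis for a stated secondary question. Section 3.2 asks about variation in effect over days, and section 15.3 contains no test of it. If variation were read from the pattern of daily significance, a constant 20% effect would look variable in about 44 to 61% of trials with 7 days and 28 to 44% with 3 days, against about 5% for a group-by-day test. The rates rest on the assumed correlations, equal daily means and SDs, normal doses and complete days; the documents give none of the daily figures. Across these settings they remain well above 5%.

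The result does not show that the true effect is constant, or that the investigators will misread the daily results. The primary comparison and the safety monitoring are unaffected. It is a cheap improvement to a secondary analysis.

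**What to change.** In section 15.3:

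- Add opioid dose per kg by post-operative day to the outcomes analysed by mixed-effects models, with group, day, group × day, transplant type, age and gender, and within-child correlation.
- State the scale in advance: mg/kg if the question is about absolute sparing, or a log or ratio scale if it is about percent reduction.
- State that the section 3.2 question is answered by the group × day term or by one pre-stated early-versus-late contrast. In step 5 of the working the single contrast has about twice the power of the 6-df test for a modest change.
- Report per-day differences as estimates with 95% confidence intervals, without day-by-day significance claims.
- Say how days after PICU transfer are handled, since later days will not exist for every child.

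The cost is a few sentences and one model on data already collected. The downside is limited power at 60 versus 30 for anything short of a marked change, so the time pattern will often be reported as uncertain.

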## MEDICAL PROTOCOL (HRP-590)

PROTOCOL TITLE: Magnesium sulfate as adjuvant analgesia and its effect on opiate use by post-operative transplant patients in the pediatric ICU.

VERSION DATE: 06/09/2022

interpret and do not always correlate well with true comfort measures. Other data collection listed below will be used to help track safety data regarding magnesium effects, correlations between magnesium level and opioid variables, other analgesic dosing, as well as general statistical comparisons such as sex, type of surgery, and age. A list of data measures is provided in a secondary attachment with this protocol.

### 4. Study Intervention(s)/Investigational Agent(s)

4.1. Description: MgSO4 is a pharmacological agent which will be administered intravenously as a 30-minute bolus dose of 50 mg/kg (maximum 2 grams) in the OR, followed by a 15 mg/kg/hr IV infusion for an additional 48 hours or once the patient has transferred out of the PICU, whichever comes first. The bolus will be given after anesthesia induction for TPIAT patients, and after reperfusion of the transplanted liver for liver transplant patients (this is deemed by surgeon to pose less hemodynamic risk). Of note, it is not anticipated that our patient population would leave the PICU prior to 48 hours. Standard bolus dosing of MgSO4 in pediatrics is 25-75 mg/kg, so per the above literature search 50 mg/kg seems a confirmed safe dosing. Similar dosing protocols using a bolus and infusion which have been studied for analgesia in children without side effect in the literature include the following: 50 mg/kg then 15 mg/kg/hr (18,20), 30 mg/kg then 10 mg/kg/hr (14,25), 50 mg/kg then 8 mg/kg/hr (17). Our proposed 50 mg/kg + 15 mg/kg/hr infusion dose has been utilized effectively and safely at the adult level as well (5,49). Dosing as high as 100 mg/kg then 40 mg/kg/hr has been used in tetanus. To our knowledge, MgSO4 for analgesia remains 'off-label' use, unless discussing for headache pain (used commonly in emergency room medication 'cocktails' for migraines). It is known however that magnesium acts antagonistically on the NMDA receptor, a common nociceptor, one also targeted by ketamine (1). MgSO4 will be delivered at concentration of 100 mg/mL via patient's central line (placed in all transplants regardless of study intervention). MgSO4 is also a physiologically vital electrolyte in the human body, and one that is replaced frequently in the ICU, including in the post-operative transplant population. To avoid nearing toxic magnesium levels, we will titrate medication dosing to be below 3.5 mg/dL. Total magnesium level will be checked in the OR following bolus dose, every 2 hours throughout the transplant procedure, at the initial PICU transfer and every 4 hours [expected window +/- 1 hour] for the remainder of infusion. Other electrolytes (including potassium, ionized calcium, phosphorus) will be checked at least daily (sometimes more if deemed appropriate for other standard of care transplant requirements, which is typically every 6 hours). If any magnesium level is above target, infusion dose will be decreased by 5 mg/kg/hr. These adjustments are based on pharmacokinetic-pharmacodynamic data and pharmacist expertise at the UMN. If magnesium infusion is at any time decreased to 0 mg/kg/hr based on these levels, it will not

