## MEDICAL PROTOCOL (HRP-590)

PROTOCOL TITLE: Magnesium sulfate as adjuvant analgesia and its effect on opiate use by post-operative transplant patients in the pediatric ICU.

VERSION DATE: 06/09/2022

transplant and particularly TPIAT patients, we intend to implement a combination of intra-operative and post-operative magnesium protocol. To our knowledge there is no definitive therapeutic window for magnesium's analgesic effect, and studies vary as to what supra-physiologic levels are obtained based on their derived infusion protocol. Comparable intra-operative infusion doses in pediatric analgesic studies range from as low as 30 mg/kg + 10 mg/kg/hr (25) and 50 mg/kg + 8 mg/kg/hr (17) to as high as 50 mg/kg + 15 mg/kg/hr (18). The study at our proposed dosing had levels of 3.2 mg/dL immediately post-op (18). Infusions of higher doses have been used safely in pediatric asthma studies, including doses of 50-75 mg/kg + 40 mg/kg/hr for 4 hours, reaching interquartile levels of high 3's to mid 4's mg/dL (37). In adult studies prolonged infusions have been used for subarachnoid hemorrhage targeting higher ranges of 4-6 mg/dL for up to 10 days duration (38,39). Adult studies have also demonstrated efficacy in infusion protocols beyond the operative period (40,41). One protocol of 30 mg/kg + 10 mg/kg/hr was used for 48 hours in thoracotomy patients with levels of 2.8 +/- 0.3 mg/dL at conclusion (41). Prolonged infusions in pediatrics beyond 24 hrs in the literature to our knowledge exist only in asthma studies, including one with average duration of ~4 days (42). None of the above studies encountered any clinically significant magnesium side effects, and only transient diplopia and muscle weakness was reported in the adult subarachnoid hemorrhagic study when levels reached 6 mg/dL (symptoms resolved with lowering dose).

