According to DynaMED and Micromedex searches on magnesium, normal levels may range 1.5 - 2.5 mEq/L (equivalent to 1.8-3.1 mg/dL), and toxic hypermagnesemic levels are typically not seen until >4 mEq/L (4.86 mg/dL), which does not yet include many of the hemodynamic and EKG changes (typically at >5 mEq/L or 6.08 mg/dL). Most background data in our referenced sources cite ~4.5-5 mg/dL as potential sources of clinically relevant magnesium toxicity. We intend to target levels well below this and will avoid adverse effects by checking serial magnesium levels and titrating our infusion dose down if needed. Level checks and titration plan is determined from existing pharmacokinetic/pharmacodynamic data, discussions with our pharmacy team, which is standardly involved with safety modifications of all admitted PICU patients, and recommendations from the FDA during the IND process. The significance and rationale for this study has been alluded to above, namely due to the extensive pain that post-operative transplant children endure, and our clinical duty to treat this medical problem (benevolence). Our post-operative patients are scheduled on a number of analgesic modalities simultaneously, including acetaminophen, NSAIDs, opioids, ketamine, non-pharmacologic intervention (child life, music therapy, etc), and even procedural (paravertebral block in TPIAT patients) - stressing both the difficulty of their pain control as well as the need for safe alternatives. Additionally, the growing threat of the opioid crisis and shortage has emphasized the need for adjuvant analgesic options in a multitude

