## 13. Risks to Participants

*13.1. Foreseeable Risks:* This would include the potential for known side effects from magnesium toxicity, namely: hypotension, cardiac arrhythmia, hyporeflexia, effects on other electrolytes (such as potassium and calcium), muscle weakness, respiratory depression (secondary to muscle weakness), and increased sedation (including when combined with opioids and benzodiazepines). These toxic risks are cited typically at levels of > 4-4.5 mg/dL. We will minimize this risk by targeting magnesium thresholds below this. Hypotension is monitored for via routine serial blood pressure monitoring in all ICU patients, and can be treated with IV fluid resuscitation as needed (standard for hypermagnesemia treatment). Cardiac arrhythmia is monitored for via cardiac telemetry in all ICU patients, and cardiology specialists and arrhythmia resuscitation techniques are available per standard ICU care. Both of these are risk factors that are present in these populations regardless of magnesium use, however if these conditions are felt potentially contributed to by hypermagnesemia the infusion will be stopped for further evaluation. Electrolyte abnormalities are also common in ICU populations and are monitored routinely per post-transplant protocols. Respiratory depression is monitored routinely in this population as well, however if secondary to perceived muscle weakness out of proportion to standard post-operative course, the magnesium infusion will be stopped as well. Sedation and other analgesia is routine in post-operative transplant care and is addressed and titrated based on daily goals. Decreasing other sedatives will take precedent over magnesium in cases of oversedation given the overall objective of the study. Increased blood draws may occur during monitoring, however in 48 hours of infusion may result in only 4-8 mL of extra blood specifically from magnesium draws alone, which clinically seems insignificant relative to overall course. There is potential for dosing error as is for all PICU delivered medications, however correct units for MgSO4 has been updated in UMMCH pump library, and there is additionally standard ICU regulations per institutional and leadership for routine drip/dose checks. The only other potential foreseeable risk would be that of intravenous line capability. Post-operative transplant patients require multiple IV

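### At 15 or 10 mg/kg/hr, section 4.1 requires the same 5 mg/kg/hr decrease for every level above 3.5 mg/dL, including levels the plan itself calls toxic

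*Combined protocol and SAP*

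**What the plan says.** Section 4.1 gives a 50 mg/kg bolus in the OR, then 15 mg/kg/hr for up to 48 h, with titration to keep the level under 3.5 mg/dL. Levels are drawn after the bolus, every 2 h in the OR, on arrival in the PICU, and then every 4 h with a window of 1 h either way.

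The level-based rule is: "If any magnesium level is above target, infusion dose will be decreased by 5 mg/kg/hr". The level-based end point follows: "If magnesium infusion is at any time decreased to 0 mg/kg/hr based on these levels", the drug is not restarted. Section 12.1 lists serial reduction to zero as a ground for withdrawal. Section 18.1 lets the attending or fellow change the dose under the protocol when the level exceeds 3.5. The hypermagnesemia item in 18.2 uses the same 3.5 and asks for confirmation that the dose was lowered. None of these adds a higher threshold.

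On toxicity, section 2.3 says "Most background data in our referenced sources cite ~4.5-5 mg/dL as potential sources of clinically relevant magnesium toxicity". It also gives 4.86 mg/dL as the level above which toxicity is typically seen, with many of the hemodynamic and EKG changes typically above 6.08. Section 13.1 says "These toxic risks are cited typically at levels of > 4-4.5 mg/dL".

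On the basis for the rule, 4.1 says "These adjustments are based on pharmacokinetic-pharmacodynamic data and pharmacist expertise at the UMN", and 2.3 adds "recommendations from the FDA during the IND process".

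**The concern.** The size of the excess does not change the required action. At 15 or 10 mg/kg/hr, a result inside the plan's own toxic range calls for one step down, after which the infusion continues at 10 or 5 mg/kg/hr until another level is drawn and acted on. Titration is the plan's stated means of staying clear of toxic levels, yet the text does not say what to do when a result is already there. A child with such a level and no recognised sign would, under the written rule alone, stay on a reduced infusion. Section 4.1 acknowledges that this population has not been studied before.

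**Working it through.** **Reproducing the plan's figures.** mg/dL = mEq/L × (24.305 / 2) / 10, where 24.305 is the atomic weight of magnesium. This gives 4 mEq/L = 4.861 mg/dL and 5 mEq/L = 6.076 mg/dL, matching the 4.86 and 6.08 in section 2.3.

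**Distance from the trigger to the toxic range.** Using 13.1: 4.0 − 3.5 = 0.5 and 4.5 − 3.5 = 1.0 mg/dL.

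**Inputs (section 4.1).** Rate 15 mg/kg/hr; step 5 mg/kg/hr; interval 2 h in the OR and 4 h ± 1 h in the PICU. Above-target results needed to reach zero: three from 15, two from 10, one from 5.

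**Dose after the first high level.** Assume that every later level is above 3.5, that nobody uses discretion and that enough of the 48 h remains. Count time from draw to draw, because no laboratory turnaround is given. With draws at s0, s1 and s2:

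- From 15: dose = 10 × (s1 − s0) + 5 × (s2 − s1).
- From 10: dose = 5 × (s1 − s0).

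| Setting | Start rate | Time | Further dose |
|---|---|---|---|
| PICU, 4 h intervals | 15 | 8 h | 10×4 + 5×4 = 60 mg/kg |
| PICU, window on each interval (3-5 h) | 15 | 6-10 h | 15×3 = 45 to 15×5 = 75 mg/kg |
| PICU, window on each draw | 15 | 6-10 h | 10×2 + 5×4 = 40 to 10×6 + 5×4 = 80 mg/kg |
| PICU, 4 h intervals | 10 | 4 h | 5×4 = 20 mg/kg (15-25 by interval, 10-30 by draw) |
| OR, 2 h intervals | 15 | 4 h | 10×2 + 5×2 = 30 mg/kg |
| OR, 2 h intervals | 10 | 2 h | 5×2 = 10 mg/kg |
| Either | 5 | 0 h | 0; the step stops the drug |

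For comparison, an unchanged 15 mg/kg/hr would give 15×8 = 120 mg/kg in the PICU and 15×4 = 60 in the OR, so the existing steps halve the dose (60/120 = 30/60 = 0.50). An immediate stop makes every entry 0 on the same time count. Section 4.1 allows a missed draw to be taken late, so 10 h is not a firm ceiling. If the next level is not above target, the infusion continues at the reduced rate.

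**Do the other stops cover a high level alone?**

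- 4.1: off at once for an adverse event in which magnesium is suspected. Under the 18.2 definitions an abnormal result can count as an adverse event, for example if the investigator judges it significant or if it leads to more tests or treatment. This needs a judgment; no level is named.
- 12.1: halt for confirmed low blood pressure or persistent bradycardia; stop for over-sedation only after other sedatives have been lowered where possible; optional withdrawal for a laboratory abnormality.
- 13.1: stop for arrhythmia or hypotension thought related to hypermagnesemia, or for respiratory depression from weakness.
- 18.1: the study team may direct order changes, and the infusion is paused in the OR if anesthesia cannot draw a level or adjust the dose.

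Each depends on an event or on discretion. None gives a magnesium level.

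**The case against.** The case for leaving the rule alone has substance.

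- **High levels should be uncommon.** Section 2.3 reports 3.2 mg/dL after surgery at this dosing, and 2.8 ± 0.3 after 48 h of a lower-dose adult regimen. Levels up to the mid 4's in pediatric asthma came from 40 mg/kg/hr, about 2.7 times this rate (40/15). Section 8.2 excludes preoperative creatinine above 1.5 times the upper limit of normal.
- **Moderate excess was tolerated in cited studies.** In the adult hemorrhage study, symptoms at 6 mg/dL resolved when the dose was lowered.
- **People are watching.** Under 18.1 a study team member checks in at each dosing change, is always reachable, and follows up each OR level. The worst case needs these contacts to produce no further action.
- **The rule has a pedigree.** Pharmacy and FDA input lie behind it, and the documents do not show whether a graded rule was considered.

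All of this limits the likelihood and the weight of the point. It does not supply the missing instruction: the check-in at a dosing change confirms the step without telling anyone to go further. The tolerability data come from other populations and bear mainly on where the cut-off should sit. The further dose in mg/kg measures exposure, not harm.

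A reader might infer that the plan has no immediate stop, or no level-based stop. The documents do not support either reading: 4.1 stops the drug at once for a suspected magnesium-related event, and a level above 3.5 at 5 mg/kg/hr ends it permanently.

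**Conclusion.** The point holds at 15 and 10 mg/kg/hr: no magnesium level by itself mandates an immediate stop at those rates, and a toxic-range result requires one step. The largest nominal consequence is 60 mg/kg over 8 h in the PICU, conditional on persistently high levels, no discretionary action and enough infusion time left. A reader might go further and infer that children are likely to reach toxic levels or be harmed. The documents give no probability for this case and no basis for saying how far a level would rise, and they place many of the more serious effects above 6.08 mg/dL. This is a modest safety improvement that the sponsor should make because it is cheap, not evidence that the dosing is unsafe.

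**What to change.** Keep the 5 mg/kg/hr step for levels above 3.5 and below 4.5 mg/dL. Add the following to 4.1, and mirror it in 18.1 and in the hypermagnesemia check in 18.2:

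- At 4.5 mg/dL or more, turn the infusion off at once, notify the study team and safety monitor, and continue levels at the existing study interval. The 4.5 is the plan's own figure; pharmacy and the sponsor may confirm 4.86 instead.
- Restart only when the level is below 3.5 mg/dL and investigation finds it safe, at a rate at least 5 mg/kg/hr lower than before the hold.
- If an adverse event is attributed to magnesium, the existing indefinite-discontinuation rule in 4.1 applies instead.
- A hold for level alone, without a clinically significant reaction, does not count toward the two-patient halt in 3.1 and 12.3, and is not the permanent zero-rate end point. At 5 mg/kg/hr the existing permanent stop continues to apply.

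The cost is a protocol and IND amendment, an order-set edit, and some lost study drug in a few children, for example at a brief peak after the bolus. No extra patients are needed, and no draws beyond the existing schedule. Section 15.3 already keeps children with discontinued magnesium in the experimental group, so the analysis plan does not change.
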